FamTechCare Clinical Trial

[name], PhD
NCT02483520

**Supporting Family Caregivers with Technology for
Dementia Home Care (FamTechCare)**

Protocol & Statistical Plan
Last IRB Approval Date: July 7, 2016

B. APPROACH. The proposed study combines randomized clinical trial (Aim 1) and descriptive (Aim 2) designs with cost efficiency analysis (Aim 3) to evaluate the multi-component FamTechCare intervention. FamTechCare uses new technology for caregiver initiated recording of PWD behavior that also captures video of precursors to behaviors and precipitating factors. Videos are automatically uploaded to HIPAA-secure storage for review by a team of dementia care experts who analyze the rich data and provide individualized just-in-time, interventions. An overview of the aims is provided first and details follow in sections below.

Aim 1. A randomized clinical trial with repeated measures will be used to test effects on PWD and caregiver outcomes. Dyads will be randomly assigned to an intervention or an attention control group at each site. Linear mixed modeling with post-hoc comparisons will be used to compare between-group and within-subject outcomes at 1 and 3 months to determine intervention effects on objective PWD and caregiver-reported outcomes. Behavior coding using our established protocols will provide objective measurement of disruptive behaviors (Williams et al., 2009). Behavior coding of post-intervention recordings will also be used to measure caregiver intervention use and effects on behaviors. Caregiver-reported stress, burden, depression, sleep, and confidence in providing care will also be compared. Linear mixed modeling provides examination of each variable to determine its effect size over time and also to determine which outcomes are most sensitive to the intervention.

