D1. Sample. Eighty-eight dyads will be recruited from the University of Iowa Hospitals and Clinics (UIHC) and the University of Kansas Alzheimer's Disease Center (KU ADC). KU ADC is the area's major referral center with a clinic evaluating more than 300 new and 600 total patients annually. UIHC is the state and regional leader in tertiary care, providing research and clinical specialty care in Geriatric Psychiatry and Memory Disorders. It is estimated that 50% of family caregivers request professional assistance for managing disruptive behavior; so adequate study recruitment and enrollment is anticipated. If enrollment is not adequate, other dementia care providers (i.e. Alzheimer's Association) will be contacted.

Inclusion criteria for PWD are a diagnosis of AD or other dementia (moderate stage) and residing with a family caregiver who reports disruptive behavior management issues. Exclusion criteria include Huntington's disease, alcohol-related dementia, schizophrenia, manic-depressive disorder, deafness, and mental retardation. Participants with dementia of varied etiology will be included (a covariate factor). Electronic medical record search tools and dedicated research team time will facilitate identification of eligible participants. A trained research assistant (RA) will perform a Functional Assessment Staging of Dementia to confirm moderate dementia (Sclan & Reisberg, 1992) and the each caregiver will complete the Revised Memory and Problem Behavior Checklist (Roth et al., 2003) to verify the presence of disruptive behaviors on the initial home visit.

D2. Power. Sample size for this study was determined using power analysis for the primary hypothesis. The proposed sample size will provide sufficient power to detect between-group differences in outcomes (changes in proportions of behaviorally coded disruptive behaviors of PWD). In our previous research (Williams et al., 2009), the probability of PWD disruptive behaviors decreased from 55% to 26% when nurses used normal talk with PWD instead of elderspeak (patronizing communication similar to babble). We anticipate a similar 29% average decrease in the proportion of disruptive behaviors after the FamTechCare intervention. Applying this effect size as the difference between groups with a standard deviation of 35% in both and assigning a Type 1 error of 0.05 results in 93% power for detecting group differences after 3 months in 70 dyads (35 per group).

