FamTechCare Intervention. The telehealth nurse will review videos submitted by caregivers within 24 hours to facilitate emergency referrals (delirium, for example). FamTechCare caregivers will receive same-day nurse feedback (using standardized interventions) based on evidence-based protocols (see appendix C) developed by team experts and in the feasibility study (Niedens, 2010; Williams et al., 2012). Individualized, contextually-based interventions developed by the expert team (see examples in appendix D) will be provided to caregivers in their home at least weekly (after each video review meeting).

The telehealth nurse will review and select videos, leading the interdisciplinary team meetings for video review and intervention planning and will interact weekly with caregivers to provide feedback. The internet-based team meetings will be conducted using Zoom HIPPA-secure teleconferencing that supports live, interactive videoconferencing from different locations. Zoom teleconferencing is accessed using a unique weblink to a secure meeting. Using a share screen feature, all group members can watch the videos and simultaneously discuss and develop interventions.

Interventions will be documented on a behavioral care plan form modeled after other studies, providing individualized intervention instructions for a specific disruptive behavior (Burgio et al., 2009). Interventions will initially focus on nonpharmacological interventions. For example, pain interventions may first focus on assisting PWD to report pain, identify person-specific indicators of pain for caregivers to monitor, and teach pain control measures such as relaxation, distraction, and massage to the family caregiver. Our interdisciplinary team includes clinicians and investigators from KUMC and UIHC in partnership with a social worker from the Alzheimer's Association, and home-care nurses. Additional experts, such as a pain management nurse and speech and occupational therapists are available as needed to review videos.

Control Intervention. The control intervention is designed to be equivalent to FamTechCare for time and attention. Control group videos will be held for review and feedback after 3 months. Control caregivers will receive a weekly phone call from the nurse, who will provide standardized disruptive behavior management guidelines per protocol (see appendix C) (Niedens, 2010).

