Behaviorally Coding of Disruptive Behaviors will be completed using our behavioral coding protocols from our NIH-funded R03 and R01 studies (Herman & Williams, 2009; Williams et al., 2009). We will use the Noldus Observer Video Pro (2003) software program to code disruptive behaviors, based on the operational definitions in the Resistiveness to Care scale (Mahoney et al., 1991). A computer key corresponding to each behavior state (disruptive or cooperative) is depressed when behaviors occur in the real time video recordings. Duration of each behavior state (disruptive or cooperative) is tabulated by the length of time keys remain depressed (until the key corresponding to the alternate, mutually exclusive behavior state is pressed). RAs will be trained using our protocol operational definitions for disruptive behaviors on practice materials until inter-coder agreement reaches 90% or greater. As in our prior studies, we will assess inter-coder agreement on 10% of actual study data. Retraining of coders will be provided if reliability falls below targets. RAs coding video will be blind to group and time of collection. Three recordings of videos of each priority care activity submitted at baseline, 1, and 3 months will be analyzed. The proportion of time disruptive behaviors occur will be compared within individuals and changes in the proportion of disruptive behavior compared between groups.

Caregiver-report Disruptive Behaviors. The 31-item Revised Memory and Problem Behavior Checklist (RMPB). (Roth et al., 2003; L. Teri et al., 1992) elicits caregiver reports of the behavior frequency related to 24 memory, depression, and disruptive behaviors in the past week, with Cronbach's alpha of .785.

PWD Stress. We hypothesize that FamTechCare interventions will reduce disruptive behaviors as well as stress in PWD.

PWD Medication Use. Counts of caregiver reported elective (prn) use of anxiolytics, hypnotics, and antipsychotic drugs taken by PWD in the past week will be compared between groups at 1 and 3 months.

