The fixed effects in the model will include group (FamTechCare or control), site (UIHC or KU ADC), data collection time (baseline, 1, or 3 months), and all two-factor and three-factor interactions, including treatment by time interaction. A significant treatment by time interaction effect will indicate differences between the two groups. The analysis will be adjusted for important covariates, identified with baseline comparisons. With 70

subjects, 7 covariate factors meet statistical requirements for 5 to 10 subjects per covariate (Tabachnik & Fidell, 2001).

Fit of the models will be assessed using appropriate fit statistics, including Akaike information criterion (AIC) and likelihood ratio tests. To test for specific comparisons of interest, i.e. comparing treatment and control groups in terms of their mean change in PWD's disruptive behaviors, stress, and psychoactive medication use and caregivers' stress, burden, depression, sleep, and confidence (e.g., from baseline to month 3), tests of mean contrasts will be performed using parameter estimates from the fitted mixed models. Significant differences between the two groups, if they are in the expected direction, will support the hypothesis. An additional model per protocol will test changes in outcomes using only dyads in which the caregiver used recommended interventions in subsequent video recorded interactions.

D9b. Specific Aim 2. Identify precursors of disruptive behaviors and develop a typology of interventions for caregiver in-home use. We will use content analysis of caregiver submitted videos and recorded team video review meetings to tabulate the most common symptoms and behaviors. Qualitative content analysis of recorded team meetings for video review and written intervention plans for caregivers will identify key symptoms and behaviors. We will also code behaviors and symptoms exhibited by PWD in pre- and post-intervention videos submitted by caregivers. Counts will be analyzed descriptively to identify the most common symptoms and behaviors and the recommended interventions and their effectiveness.

D9c. Specific Aim 3. Evaluate ease of use, satisfaction, and cost effectiveness of FamTechCare using traditional cost methods and Data Envelopment Cost-efficiency Analysis (DEA).

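### The Aim 1 model leaves the baseline outcome free rather than adjusting for it, which costs precision, and no single test is named as deciding the primary hypothesis

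*Combined protocol and SAP*

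**What the plan says.** D9, Specific Aim 1, specifies a linear mixed model whose fixed effects are group, site, "data collection time (baseline, 1, or 3 months), and all two-factor and three-factor interactions, including treatment by time interaction". Further adjustment is for covariates picked from baseline group comparisons. The candidates listed in D6 and D9 are features of the dyad, the dementia, the caregiver and the site. The baseline value of the outcome is not among them.

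On the deciding test, D9 first states: "A significant treatment by time interaction effect will indicate differences between the two groups". It then says that, for specific comparisons of mean change, "tests of mean contrasts will be performed using parameter estimates from the fitted mixed models", with baseline to month 3 given only as an example. Significant differences in the expected direction are to support the hypothesis. The Aim 1 overview in section B puts it differently: "Linear mixed modeling with post-hoc comparisons will be used to compare between-group and within-subject outcomes at 1 and 3 months".

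D2 describes the powered outcome as "changes in proportions of behaviorally coded disruptive behaviors of PWD". It then applies a 29-point difference and an SD of 35% in each group, which "results in 93% power for detecting group differences after 3 months in 70 dyads (35 per group"). It does not say whether the SD belongs to the change or to the value at a visit.

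**The concern.** There are three linked points.

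1. With baseline as a free response level, the baseline-to-month-3 group contrast is, with complete data, a difference in raw change scores. Randomisation makes the expected baseline means equal, and the model does not use that fact. Precision is lost on the primary outcome and on each caregiver outcome measured at baseline, although the baseline data are already collected.
2. With three times, the group-by-time interaction has 2 degrees of freedom and the month-3 contrast has 1. The two can disagree. The word post-hoc in section B suggests that the interaction comes first; the month-3 power statement in D2 suggests the contrast. If the choice is left open, it can be made after the results are seen.
3. Whether the stated power applies to the planned contrast depends on what the 35% SD measures.

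**Working it through.** **Inputs.** From D2 and D3: difference 29 points, SD 35 points, α = 0.05 (taken as two-sided), 35 dyads per group analysed and 44 per group enrolled. Assumed: the baseline-to-month-3 correlation ρ, which the documents do not give, shown over 0.2 to 0.7; equal variances at the two visits.

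**The plan's own figure.** The standard error is 35 × √(2/35) = 8.37, and 29/8.37 = 3.47. Power is 92.7% by the t-test (68 df) and 93.4% by the normal approximation. The stated 93% therefore reproduces as a 1-df comparison of two means.

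**Variance cost of the free baseline.** Let s be the SD at a visit.

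- Change-score contrast: SD = s√(2(1−ρ)).
- Baseline-adjusted contrast: SD = s√(1−ρ²).
- Variance ratio: 2(1−ρ)/(1−ρ²) = 2/(1+ρ), which is 1.54, 1.33 and 1.18 at ρ = 0.3, 0.5 and 0.7.

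Put as dyads, 70(1+ρ)/2 = 45.5, 52.5 and 59.5 adjusted dyads match 70 under the planned model. Simulation with site interactions averaged over sites gave ratios of 1.52, 1.32 and 1.16.

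**Dropouts.** Suppose 44 − 35 = 9 dyads per group give baseline only and the likelihood uses them. The free contrast then has variance 2s²[(1−ρ²)/35 + (1−ρ)²/44], and the contrast with equal baseline means has 2s²(1−ρ²)/35. The ratio is 1 + (35/44)(1−ρ)/(1+ρ) = 1.43, 1.27 and 1.14. The loss shrinks but remains.

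**Power for 29 points, 35 per group** (t-test; 67 df when adjusted):

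| ρ | Visit SD 35: planned | Visit SD 35: adjusted | Change SD 35: planned | Change SD 35: adjusted |
|---|---|---|---|---|
| 0.2 | 77% | 94% | 93% | 99% |
| 0.3 | 82% | 95% | 93% | 99% |
| 0.4 | 88% | 96% | 93% | 98% |
| 0.5 | 93% | 98% | 93% | 98% |
| 0.6 | 97% | 99% | 93% | 97% |
| 0.7 | 99% | 99.8% | 93% | 96% |

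In the last column the adjusted SD is 35√((1+ρ)/2). Under the visit-SD reading, keeping the 9 baseline-only dyads per group lifts the planned contrast to 82%, 86% and 90% at ρ = 0.2, 0.3 and 0.4 (normal approximation).

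**The two candidate tests.** Take a change SD of 35, a month-3 effect of 29, and a correlation c between the month-1 and month-3 changes. Each change contrast has variance (2/35) × 35² = 70. The 2-df F test (2, 67 df) has this power:

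| Month-1 effect | c = 0.3 | c = 0.5 | c = 0.7 |
|---|---|---|---|
| 0 | 90% | 95% | 99% |
| 14.5 | 88% | 87% | 89% |
| 29 | 97% | 95% | 92% |

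The 1-df month-3 contrast has 93% throughout, so neither test is always stronger. At c = 0.5 with a month-1 effect of 14.5, the noncentrality is (14.5² − 14.5 × 29 + 29²)/(70 × 0.75) = 630.75/52.5 = 12.0. That equals the 29²/70 = 12.0 of the single contrast, so the second degree of freedom is spent for nothing.

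By simulation, counting success on either test gives a type I error of 7.3–7.7%. Requiring both gives 86–93% power over the same grid.

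**The case against.** The planned contrast is unbiased under randomisation, a repeated-measures model with baseline as a time level is conventional, and the plan speaks of change throughout. The stated sample size and power are not in error. All of this stands: the first point concerns efficiency, not validity.

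The wording of D2, read in sequence, favours the SD of change. On that reading the plan meets its 93% target, and the shortfall needs both the other reading and ρ below about 0.5. This is a fair limit on the power shortfall. It does not remove the precision loss, which is present under either reading.

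No sentence says that a win on either test is enough. If contrasts follow only a significant interaction, a month-3 claim has a type I error of about 2.5%. D9 also allows for adjusting p-values for the number of tests. The inflation is therefore conditional on how the rule is read. But D9 does not make the contrasts depend on the interaction, and its adjustment clause names neither a family of tests nor a method.

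D5 describes random assignment before the home visit at which baseline measures are taken, so baseline may not be wholly free of allocation. Any such effect would disturb the planned change contrast as well, so it does not favour the current model. It does mean that the timing of baseline needs stating.

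**Conclusion.** The concern holds and should be acted on. The free baseline inflates the variance of the month-3 contrast by 1.18 to 1.54 for ρ from 0.7 to 0.3 with complete data, or 1.14 to 1.43 with 9 baseline-only dyads per group. The loss shrinks as ρ rises. In power, this is 93% against 96–99% if 35% is the SD of change. If it is the SD of a visit value, it ranges from 77% against 94% at ρ = 0.2 to near equality at ρ = 0.7.

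The deciding test is not named, and section B, D2 and D9 point in different directions. The type I error of 7.3–7.7% applies only if either test may count.

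These figures rest on assumed correlations and equal variances; the results on the two tests also assume a correlation between changes. D9 leaves the covariance structure and any transformation open.

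**What to change.** In D9:

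- Model months 1 and 3 as the responses, with group, time, group × time, site and baseline value × time, and an unstructured covariance. Alternatively, keep baseline as a response and constrain the group means to be equal there.
- Name one group contrast at month 3, averaged over sites, as the test of the primary hypothesis. Make the 2-df interaction, the month-1 contrast and group × site × time secondary.
- Define the baseline videos as those recorded before any intervention feedback. D7a says only "Three recordings of videos of each priority care activity submitted at baseline, 1, and 3 months will be analyzed", while D4 says "FamTechCare caregivers will receive same-day nurse feedback", so the end of the baseline period is not fixed. State also when the caregiver-reported baseline measures are taken relative to assignment.

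In D2, state whether the 35% SD is of the change or of the visit value, and give the assumed baseline-to-month-3 correlation.

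The cost is wording in D9 and D2. No added dyads, visits or measures are needed.

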D5. Procedures. Each site will identify potential participants and obtain consent. As soon as 4 participants are enrolled at each site, 2 will be randomly assigned to FamTechCare and the other 2 to the Control group. This is repeated until 11 cohorts are completed. A trained research assistant (RA) will make a home visit to collect demographic data and to complete FAST staging (Sclan & Reisberg, 1992) to confirm that the PWD has moderate stage dementia. Each caregiver will complete the Revised Memory and Problem Behavior Checklist (RMPBC) to verify the presence of disruptive behaviors. The RA will assist caregivers in identifying their 3 most problematic disruptive behaviors/care situations (see D7a) as the focus for recordings and interventions and the HMU will be set up in the area where the most disturbing disruptive behaviors usually occur (as the focus for the first week). The RA will train caregivers in HMU use and provide reference books. Visits will continue until caregivers demonstrate proficiency in recording and moving the HMU using a competency checklist. If the needed, the RA will make a home visit to assist the caregiver in moving the HMU in subsequent weeks.

Caregivers will be asked to record at least one video of their identified priority disruptive behavior/care activity each day. The telehealth nurse will monitor submitted videos and prompt caregivers with reminders if needed.

Caregivers will repeat recordings of each priority disruptive behavior/care activity after using FamTechCare interventions and at 1 and 3 months. Home visits to repeat data collection will be made at 1 and 3 months in both groups.

D6. Descriptive Data. Information about caregivers and PWD that may influence study outcomes will be collected and included as covariate factors (Unruh & Wan, 2004; Yu, Evans, & Sullivan-Marax, 2005; Zimmerman et al., 2005). PWD data will include gender and dementia etiology. Data on caregiver age, competency, relationship to the PWD, and research site will also be collected for covariate analysis.

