Preliminary Analyses. Initial data analysis will involve calculating descriptive statistics for all variables, at all data collection points, including means and standard deviations for continuous variables and frequencies and proportions for categorical variables. Outliers will be investigated for accuracy and possible entry errors. Graphical representation of the data and correlations among variables will be examined. The distributions of continuous variables will be evaluated for normality and homogeneity of variance and appropriate transformations will be applied as needed, or statistical analyses for non-normal data will be utilized. Patterns and site effects of missing data will be examined. A significance level of .05 will be used for statistical tests, except where p-values need to be adjusted to account for the number of tests performed.

Specific Aim 1. Determine the effects of FamTechCare on PWD and CAREGIVER outcomes at 1 and 3 months. Treatment and control groups will be compared at baseline, using appropriate tests (i.e., t, Mann-Whitney U, or Chi-square tests) to identify potential covariates found to influence NDDCB in theory and research, such as dyad relationship type (spouse, child), gender combination (male-male etc.), dementia type (etiology screen), and caregiver age (Cohen-Mansfield et al., 2005; Forbes-Thompson et al., 2006; Kovach et al., 2005; Scott et al., 2005). The outcome variables for this aim will be PWD disruptive behaviors, stress, and psychoactive medication use and caregivers' stress, burden, depression, sleep, and confidence.

A linear mixed model approach for repeated measures will be used to test differences in mean changes in the outcome variables between the treatment and control groups. By using the mixed models approach, we will be able to account for the correlation of outcome measures for the same subject across time points with the selection of an appropriate covariance structure. This analysis can handle incompletely observed subjects by using likelihood estimation methods, and provides valid estimates and tests under the assumption that the data are missing at random (Brown & Prescott, 2006).

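### D1 and D6 make baseline factors covariates outright, but D9 admits those other than site only through baseline tests between randomised groups; the baseline outcome could also add precision where it is measured before assignment

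*Combined protocol and SAP*

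**What the plan says.** **Covariates.**
- D1 (Sample): "Participants with dementia of varied etiology will be included (a covariate factor").
- D6 (Descriptive Data): "Information about caregivers and PWD that may influence study outcomes will be collected and included as covariate factors". It lists PWD gender and etiology, and caregiver age, competency, relationship and research site.
- D9 (Specific Aim 1): "Treatment and control groups will be compared at baseline, using appropriate tests", with t, Mann-Whitney and chi-square tests as examples. The purpose is to identify potential covariates among factors that theory and research link to behaviour. Four examples are given: relationship type, gender combination, dementia type and caregiver age. The adjustment rule follows: "The analysis will be adjusted for important covariates, identified with baseline comparisons".
- D9 (Preliminary Analyses): "A significance level of .05 will be used for statistical tests", except where p-values are adjusted for the number of tests. No separate cut-off is given for covariate selection.

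**Model.** The D9 fixed effects are group, site, "data collection time (baseline, 1, or 3 months), and all two-factor and three-factor interactions". Site is therefore always included, and baseline is one of the response occasions.

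**Order of events.** D5 (Procedures): "As soon as 4 participants are enrolled at each site, 2 will be randomly assigned to FamTechCare". The home visit is described after that sentence. D1 places confirmation of eligibility (dementia staging and the behaviour checklist) on the initial home visit.

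**Power.** D2 bases power on "changes in proportions of behaviorally coded disruptive behaviors of PWD", with a 29-point difference, SD 35, 35 dyads per group and a stated 93%. It does not say whether 35 is the SD of a change or of a single visit.

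**The concern.** The covariate passages cannot all be followed. An analyst working from D1 and D6 would put etiology, gender, caregiver age and relationship in every Aim 1 model. An analyst working from D9 would wait for the baseline comparisons. Under randomisation a factor is flagged at the rate of the test level, whether or not it predicts outcome, so the test is a poor guide to what deserves adjustment. What is at stake is a model fixed before the data are seen, across a long list of Aim 1 outcomes.

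The second matter is efficiency. With baseline as a response and free group means, the complete-data month-3 contrast is a plain difference in mean change. Where baseline precedes randomisation, the groups share the same expected baseline. Using that fact, by adjusting for baseline or fitting one common baseline mean, gives a more precise estimate from data already being collected.

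**Working it through.** **1. The plan's own figure.** Inputs from D2: difference 29, SD 35, 35 per group, alpha 0.05 (two-sided assumed). SE = 35 × √(2/35) = 8.367, and 29/8.367 = 3.466. The noncentral t with 68 df gives 92.7%, which agrees with the stated 93%.

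**2. Chance of being flagged.** With k independent tests at level a, P(at least one flagged) = 1 − (1 − a)^k. D9 gives four example factors; the cut-off and independence are assumptions.
- a = 0.05: 1 − 0.95⁴ = 0.185, so none is flagged in 81% of trials
- a = 0.0125 (0.05/4): 1 − 0.9875⁴ = 0.049
- a = 0.10: 1 − 0.90⁴ = 0.344
- a = 0.20: 1 − 0.80⁴ = 0.590

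Etiology alone would enter in about 5% of trials at 0.05. With 44 per arm, caregiver age is flagged only if the means differ by at least 1.988 × √(2/44) = 0.42 SD.

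**3. Effect of a covariate on the planned contrast.** A factor that is constant over time and enters as a main effect cancels from a within-dyad change. With complete data the group-by-time contrast is therefore unchanged. A mixed model fitted to one simulated dataset gave −23.046 (SE 6.634) both with and without the covariate. Under the attrition assumed in step 4, and an assumed covariate-outcome correlation of 0.3 to 0.5, the variance ratio is 0.979 to 0.999, a change of about 2% at most.

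**4. Gain from using baseline.** Let s be the one-visit SD and rho the baseline to month-3 correlation, which the documents do not give.
- Difference in change: variance proportional to 2s²(1 − rho)
- Adjusted for baseline: variance proportional to s²(1 − rho²)
- Ratio: (1 + rho)/2, below 1 for every rho below 1

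For incomplete data, assume 10% loss by month 1 and 20% by month 3 (D3 gives only the overall 20%). Of 44 per arm, 44 × 0.8 = 35.2 have all visits, 44 × 0.9 − 35.2 = 4.4 have baseline and month 1, and 4.4 have baseline only. Generalised least squares with equal correlation between visits, ignoring site, gives the attrition columns. Power takes 35 as the SD of change, with 68 df. Arrows run from the planned to the adjusted model.

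| rho | Variance cut, complete | Variance cut, attrition | Power, complete | Power, attrition | Detectable at 80% power, attrition |
|---|---|---|---|---|---|
| 0.3 | 35% | 30% | 92.7 → 98.9% | 94.5 → 98.9% | 22.8 → 19.1 |
| 0.5 | 25% | 21% | 92.7 → 97.6% | 94.2 → 97.8% | 23.0 → 20.4 |
| 0.7 | 15% | 13% | 92.7 → 96.0% | 93.9 → 96.3% | 23.2 → 21.7 |
| 0.8 | 10% | 8% | 92.7 → 95.0% | 93.8 → 95.5% | 23.2 → 22.2 |

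Example at rho 0.5, complete data: SE = 8.367 × √0.75 = 7.246; 29/7.246 = 4.00; power 97.6%. If adjacent visits correlate at √rho instead, the attrition cuts are 31%, 22%, 13% and 9%. D7a analyses three recordings per activity at each time point. If these are averaged, the higher correlations and smaller gains are more likely.

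**5. Meaning of the SD.** If 35 were a one-visit SD, the SD of change would be 35 × √(2(1 − rho)), which equals 35 at rho 0.5. Planned power would then fall below the stated figure only for rho below about 0.50 (complete data) or 0.46 (attrition).

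**The case against.** **The covariate rule has little numerical effect.** This stands. Step 3 shows almost no change in the planned contrast if covariates enter as main effects. D9 does not say how they enter, so the effect could be larger if they enter by time, but that is not established. The point rests on pre-specification and consistency.

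**D9 does not say that significance alone decides.** Partly right. D9 limits candidates to factors with theoretical support, refers to important covariates, and keeps site in regardless. D6 also speaks of collecting data for covariate analysis, which could describe a candidate pool. Even so, the adjustment sentence ties entry to the baseline comparisons, and D1 and the opening of D6 carry no such condition.

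**The flagging rates are illustrative.** Agreed. The cut-off is assumed, and relationship, age and gender combination are plausibly correlated. With an assumed correlation of 0.7 among three of the four test statistics, 19% becomes about 15%.

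**The baseline part is optional and least secure for the main outcome.** The planned model is a standard one and copes with incomplete data. Baseline videos exist only once the recorder is installed and the caregiver trained, at a visit that D5 describes after assignment. A reader might infer that baseline is collected after assignment. The documents do not establish that: D1 puts eligibility checks on the initial home visit, and the order of sentences in D5 is not a stated chronology. The order is unclear, which is why the recommendation is conditional.

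**Conclusion.** The conflict between D1/D6 and D9 is real and should be removed. It concerns etiology, gender, caregiver age, relationship and competency, but not site. Its consequence is an adjustment set that depends on chance imbalance, with a variance effect of about 2% at most for main-effect covariates under the assumed attrition.

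The baseline part is an available gain and not an error. The variance reduction of 35% to 10% (complete data) or 30% to 8% (attrition) rests on assumed correlations, loss pattern and covariance, and applies only to outcomes measured before assignment.

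A reader might infer that the planned analysis is biased, inflates type I error or is underpowered. None of these is supported. The model with free baseline means is valid. A simulation of test-based selection (single follow-up analysis, 35 per arm) gave rejection rates of 3.6% to 4.7% under no effect. The stated 93% stands if 35 is the SD of change, which the wording of D2 suggests but does not settle.

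**What to change.** 1. Delete baseline significance testing as the selection rule in D9. Baseline tables can remain descriptive.
2. Reconcile D1, D6 and D9 by fixing one covariate set for all Aim 1 models: PWD gender, etiology, caregiver age and relationship, plus site as planned. State how each enters; category groupings and gender coding are the sponsor's choice. Say whether caregiver competency is included, and include it only if it is measured before assignment.
3. State in D5, outcome by outcome and including the videos, whether baseline is collected before assignment.
4. For outcomes that are, pre-specify one model: either the baseline outcome as a covariate (by time) for the 1- and 3-month values, or a common baseline mean with group effects at 1 and 3 months. Keep the free-baseline model for the rest.
5. State in D2 that 35 is the SD of change, or give the assumed correlation.

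**Cost.** Items 1, 2 and 5 are wording, with no new data and a few degrees of freedom. Five factors including site stay within the plan's own limit of 7. Items 3 and 4 are also wording where baseline already precedes assignment. Extending the adjusted model to the video outcome might mean changing the order of recorder set-up and assignment.
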